## 1.0 Objectives

1.1 The proposed research is directly relevant to public health because it aims to target health disparities in access to behavioral health care during the COVID-19 pandemic among Black, Hispanic, and American Indian (BLAI) individuals via testing an adaptation of an established, initially validated, low-cost, mobile application ('app') designed to reduce ongoing mental health concerns among BLAI individuals with elevated anxiety and/or depressive symptoms (Easing Anxiety Sensitivity for Everyone [EASE] App). Using a precision medicine approach, EASE targets anxiety sensitivity, a transdiagnostic individual difference factor implicated in the etiology, maintenance, and progression of anxiety and depressive symptoms. EASE includes COVID-19 symptom monitoring, exposure management skills, and psychoeducation on COVID-19-related stress and the impact of stress on susceptibility to infection and disease progression; if successful, this study will provide evidence that the EASE app-based intervention can address the public health concerns of anxiety and depressive symptoms among BLAI during the COVID-19 crisis. **Aim 1.** To compare the effect of EASE with COVID-19 specific elements (n = 420) to a standard-of-care digital intervention with educational material covering stress reduction, and anxiety and depression symptom management and COVID-19 specific elements (n = 420). To evaluate the efficacy of the experimental intervention across each race/ethnic group. **Aim 2.** To identify the therapeutic mechanisms of EASE, including theoretically driven mediators (i.e., anxiety sensitivity, subsequent changes in COVID-19 related stress and fear) and moderators (i.e., perceived racial discrimination, social support, and socioeconomic status).

1.2 **H1:** Those assigned to EASE will show greater reductions in anxiety and depression symptoms, and greater reductions in functional impairment in daily responsibilities (e.g., work performance, household maintenance, and social interactions, and relationships) relative to the control group. **H2:** Effectiveness of EASE will be similar across racial/ethnic groups. **H3:** Intervention effects on study outcomes will be mediated by reductions in anxiety sensitivity and changes in COVID-19 related stress and fear. **H4:** Perceived discrimination (worse intervention outcomes), social support (better intervention outcomes), and socioeconomic status (SES; lower SES associated with worse outcomes) will be examined as potential moderators of the EASE effects.

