## **5.0 Number of Subjects**

**STUDY-WIDE:** Taking failed screeners and participant attrition into account, we expect to consent 1300 participants. We anticipate randomizing a total of 880 participants (N = 880; 220 Black, 220 Hispanic, 220 American Indian, and 220 NLW; Intervention group, n=440, control group, n=440).

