**Follow-up timeline:** Participants will complete follow-up assessments at 3- and 6-months following the baseline assessment, which will also be completed using the Insight app, in the same manner as the baseline assessment. Assessments to be conducted have been detailed below (please see 10.0 procedures involved). We expect the 3- and 6-month follow up assessment sessions will each take participants approximately 30 minutes to complete. Moreover, during the time between the baseline and 6-month follow-up assessments (6-month continuous assessment period) participants will continue to receive daily EMAs and will have access to all intervention materials included in the app.

**Project Timeline.** Year 1 will focus on obtaining IRB approval (i.e., submit application, respond to reviewers, and re-submit), hiring and training research staff, and beginning the enrollment. Year 2 will focus on recruitment, enrollment, and collecting follow-up data. Year 3 will focus on collecting follow-up data, data cleaning/analysis, and manuscript preparation and dissemination, including presenting findings at professional conferences and community-based events. For the present study, we expect approximately 50% of participants who click on our advertisement to be eligible; 75% of those who complete the phone screener to be eligible; and 95% of those to consent to participate. Weighted compensation schedule and reminder calls will be utilized to minimize subject dropout. Based on our ongoing work, we expect to enroll 39 participants each month, on average, across the 21-month enrollment period. We expect to retain 80-90% of subjects at each follow-up assessment points.

Project Timeline

ACTIVITIES TO BE COMPLETED	Year 1				Year 2				Year 3			
	Q1	Q2	Q3	Q4	Q1	Q2	Q3	Q4	Q1	Q2	Q3	Q4
HIRING AND TRAINING STAFF; STUDY PREPARATION	•											
IRB SUBMISSION AND APPROVAL	•											
ENROLLMENT AND ADMINISTER STUDY PROCEDURES		•	•	•	•	•	•	•	•	•		
DATA CLEANING									•	•		
DATA ANALYSIS & DISSEMINATION									•	•	•	•

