### **Follow-up assessments:**

Following completion of the baseline assessment, the app will automatically begin prompting twice daily EMAs for 6-months. Participants will complete two scheduled daily ecological momentary assessments (EMAs) during the intervention and continued assessment periods that will guide a just-in-time approach to immediate, personalized behavioral health care (please see EMA types section below). *Assessments will be completed remotely and no in-person study visits will be required.*

Moreover, Participants will complete follow-up assessments at 3- and 6-month post-baseline (i.e., end-of-treatment and end of 3-month continued monitoring period) using the InsightTM app. These assessments will include a qualitative interview for selected participants. The follow-up surveys will be distinguishable from EMAs (i.e., a new “Follow-up” button will appear on the app home screen (both groups) 3- and 6-month post-baseline and participants will click this button to initiate the assessment). Participants will receive a daily alert from the app to click the “Follow-up” button until the assessment is completed. Like the baseline, the follow-up assessments will include the PSS-4, PHQ-4, HRQOL, F-SozU K-6, MSSS, Covid-19 Vaccine Hesitancy Survey, Additional Aim 1 Measures, FSQ, BRFSS, Frequency of Attendance at Religious Services, Discrimination Burden, SRH, Employment Status, COVID-19 Psychological Impact Survey, Daily Activities, Change in Fast Food Consumption, Three-item Loneliness Scale, COVID-19 Substance Use, AUDIT-C, Marijuana/Cannabis Use Behavior, EDS, CRBS, SDS, PEG Scale, SSASI, OASIS, ODSIS, and Fear of COVID-19 (see above for description of measures). Additionally, the 10-item System Usability Scale will be incorporated to assess perceptions of the usability of the apps (i.e., intervention and control). Lastly, the 6-month follow-up assessment only will include two demographic questions taken from the Demographic/Background Information Questionnaire.

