**Assessment Schedule:**

Table 3. MEASURES for Phase 1

MEASURE	ITEMS	FULL BATTERY ASSESSMENTS			EMA ASSESSMENTS		
		Screen	Base	3- and 6- Month FU			
EASE Measures							
Descriptive Variables and Moderators							
Demographics-Treatment History Questionnaire (DTHQ; descriptive)	24	24			Sleep (4)		
Additional Phone Screener Items	4	4			Alcohol Consumption		
6CIT (eligibility)	7	7			Cigarette Consumption		
Rapid Estimate of Adult Literacy in Medicine-Short Form  (eligibility)	9	9			Marijuana Use		
Demographic/Background Information Questionnaire	21		21	2 (6- Month FU Only)	Fast food consumption		
Sheehan Disability Scale (SDS)  (A.1: H1)	4		4	4	Other Substance Use SSASI (2)		
System Usability Scale (A.3)	10			10	Prescription Medication Consumption		
4-item Perceived Stress Scale	4		4	4	Discrimination Experience (3)		
Everyday Discrimination Scale (EDS)  (A.2: H3)	6		6	6	Affect (15)		
					Pain Level		

**FULL PROTOCOL TITLE:** Mobile Health to Monitor Risk for COVID-19 and Improve Mental Health during the Pandemic

Coronavirus Racial Bias Scale (CRBS)  (A.2: H3)	4		4	4	Ability to Cope with Stress
The Patient Health Questionnaire-4 (PHQ-4)	4		4	4	Social Support
Health Related Quality of Life (HRQOL)	3		3	3	Location
The Perceived Social Support Questionnaire (F-SozU K-6) (A.2: H3)	6		6	6	Evening Daily Diary
MacArthur Scale of Subjective Social Status (A.2: H.4)	2		2	2	Physical Activity (2)
COVID 19 Vaccine Hesitancy Survey	15		15	15	News
Additional Aim 1 Measures	4		4	4	Money
Financial strain questionnaire	9		9	9	Hours Away from Home
Behavioral Risk Factor Surveillance System (BRFSS) Inadequate Sleep Questionnaire	5		5	5	Course of your day (2)
Frequency of Attendance at Religious Services	2		2	2	Amount eaten
PEG Scale  (A.3)	3		3	3	Argument
Affect Constructs					
Overall Anxiety Severity and Impairment Scale (OASIS)  (A.1: H1)	5	5	5	5	Pain Level
Overall Depression Severity and Impairment Scale (ODSIS)  (A.1: H1)	5	5	5	5	Ability to Cope with Stress
SSASI  (A.2: H3)	5		5	5	Location
Discrimination Burden (A.2: H.4)	4		4	4	Sunday Morning Diary
Self-Rated Health Questionnaire	33		33	21	Self-rated health questionnaire
Employment Status (A.3.b)	3		3	3	Optimism towards the future
Fear of COVID-19  (A.2: H3)	5		5	5	App Quality (3)

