COVID-19 Psychological Impact Survey	3		3	3	OASIS (5)
Daily Activities (A.1: H.1)	3		3	3	SSASI (5)
Change in Fast Food Consumption during COVID-19	1		1	1	PSI (8)
COVID-19 Substance Use (A.3.b)	4		4	4	ODSIS (5)
AUDIT-C	3		3	3	Report Distress
Marijuana/Cannabis Use Behavior	6		6	6	Affect (15)
Abbreviated Multidimensional Acculturation Scale (A.2)	15		15	15	Location
LEC5 & PCPTSD-5	6		6	6	Pain Level Ability to Cope with Stress
Three-item Loneliness Scale	3		3	3	
Mindful Attention Awareness Scale (MAAS)	15		15	15	Report COVID-19 Symptoms
Total items	273	54	209	188	Current Symptoms Exposure to someone with COVID Loss of taste/sense of smell

Note. Screen = REDCap or Phone Screener; Base = Baseline; 3- and 6-Month FU = 3- and 6-Month Post-Baseline Follow-up. \*Indicates items that are only collected during the morning EMA. \*\*Indicates items that are only collected during the evening EMA. Please see EMA types below for more information.

**EASE App Features and Treatment Components.** See Table 2 for app components. EASE offers

**Table 2.** Comparison of EASE and Control conditions

App Components	EASE	Control
EMA	X	X (add on for this study)
COVID-19 monitoring and intervention	X	X (add on for this study)
AS psychoeducation	X	
On demand tips and exercises		
Coping with mood	X	X
Coping with stress	X	X
Interoceptive exposure	X	
Guided relaxation	X	X
Inspirational messages	X	
Challenge Automatic	X	

**FULL PROTOCOL TITLE:** Mobile Health to Monitor Risk for COVID-19 and Improve Mental Health during the Pandemic

clinical grade care by integrating standard CBT with a transdiagnostic treatment for AS reduction. Individuals randomized to the EASE group will receive: 1) scheduled treatment, 2) scheduled and cued interoceptive exposure sessions, 3) on-demand intervention content (i.e., how to cope with symptoms of anxiety and depression; cognitive restructuring exercises; guided relaxation videos), and 4) tailored treatment messages based on responses to EMA items. Information about frequency of resource use and length of time spent viewing EASE intervention content will be collected through Insight™.

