*App Configuration.* The mHealth Shared Resource ([name] is the founding director) at the OUHSC and NCI Designated Stephenson Cancer Center (SCC) has developed the Insight™ mHealth Platform which enables researchers to **RAPIDLY** create studies (e.g., most studies are created within 1-2 weeks) that can use EMA and sensor data (i.e., activity monitor) to identify environmental, cognitive, affective, physiological, and behavioral antecedents of health risk behaviors (e.g., smoking, heavy alcohol use, inactivity / obesity) and deliver context-specific adaptive interventions in real-time (see more about Insight™ here: ). The mHealth resource currently employs 11 individuals, including 7 senior programmers (computer scientists/engineers) who develop and maintain our cross-platform Insight™ app and relational databases. To date, the mHealth resource has supported 65 studies including 35 with funding from the NIH. Across studies, thousands of participants have used the Insight™ app. EASE Intervention adherence will be objectively assessed by examining components used by each participant (e.g., videos watched, completed exposure exercises). To access perceived engagement with EASE and control intervention, participants will answer questions about app features used and time, in total, spent using the app each week during the Sunday morning EMA assessment. Similar methods have been used to assess app engagement in past work.

***EMA Types:*** The EMA methodology for this study will be similar to what we have used in our previous studies, and by other researchers. Each EMA will ask about current emotional, physical, and behavioral symptoms, as well as COVID-19 symptoms, and will take approximately two minutes to complete. Two types of EMAs will be used: time-based sampling (i.e., daily diary) and event sampling. Time-based EMAs will be prompted and initiated by the phone two times per day during the 6-month study period (we have had great success with this type of EMA schedule in previous trials, e.g., ~70% EMA compliance over 6 months; see Table 3 for EMA constructs). Also, participants will be instructed to self-initiate event sampling EMAs to record Distress and new COVID-19 symptoms. All EMAs will be date and time stamped for future analyses.

*Time-Based Sampling EMAs:* Daily diary EMAs will be prompted by the smartphone twice per

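### Does the hypothesis that EASE works similarly across racial/ethnic groups need a specified between-group comparison before the plan is sound?

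*Combined protocol and SAP*

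**What the plan says.** Section 1.0 states H2 as "Effectiveness of EASE will be similar across racial/ethnic groups". The corresponding part of Aim 1 is "To evaluate the efficacy of the experimental intervention across each race/ethnic group". Aim 2 and H4 name discrimination, social support and socioeconomic status as moderators; race/ethnicity is not among them.

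Section 5.0 builds race into the design with four equal recruitment cells: "220 Black, 220 Hispanic, 220 American Indian, and 220 NLW". Section 8.0 adds "We expect to retain 80-90% of subjects at each follow-up assessment points".

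On data, Section 10.0 says "Participants will complete follow-up assessments at 3- and 6-month post-baseline". Table 3 links OASIS, ODSIS, "Sheehan Disability Scale (SDS") and "Daily Activities (A.1: H.1") to the first hypothesis of Aim 1. OASIS and ODSIS are also collected in the Sunday morning diary, while the SDS is listed only at baseline, 3 and 6 months. No measure carries an H2 tag.

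The data analysis overview in Section 20.0 assigns the hypotheses of Aims 1 and 2 to latent growth, multilevel structural equation and latent difference score models. It covers estimator, missing data, model fit, baseline covariates and attrition. It presents itself as the elements common to sections that follow, but the next section in the public file is 21.0, on sharing results.

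**The concern.** Similarity of effect is a statement about contrasts between groups, and four separate efficacy results do not answer it in either direction. Equal true effects can easily produce some significant and some non-significant groups, which looks like dissimilarity. Four significant groups can hide one that gains half as much as the others. A non-significant interaction test is also weak evidence of similarity when each group has only 220 people.

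The trial is motivated by health disparities, so how EASE performs in Black, Hispanic, American Indian and non-Hispanic White participants will be read closely. Anxiety and depression are measured both at visits and weekly, so the data source for H2 is open as well as the contrast. If both were chosen after the results were seen, the same data could be described as similar, different or unclear.

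**Working it through.** The plan gives no power, effect size, SD, correlation or similarity margin, so it has no figure to reproduce. The calculation below asks how badly two simple reading rules would behave if they were used.

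**Inputs from the documents.** 220 per group (Section 5.0); 80-90% retention (Section 8.0); assessments at 0, 3 and 6 months; weekly OASIS and ODSIS; and, from the team's previous trials, "70% EMA compliance over 6 months" (Section 10.0), which gives 26 × 0.70 ≈ 18 weekly scores.

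**Assumptions not in the documents.** Arms balanced within group (110 per arm, so 99 or 88 retained); outcome SD 1; exchangeable correlation ρ = 0.5; two-sided 5% tests; a common true effect d.

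**Variance v of one group's arm effect, n per arm**

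- (a) Three-wave linear growth model, effect at 6 months, common baseline mean, partial data kept: generalised least squares gives v = 0.0147 (90% seen at both visits), 0.0160 (90% then 80%) and 0.0165 (80% at both).
- (b) Mean of the two visits, adjusted for baseline: v = (2/n)[(1+ρ)/2 − ρ²]. For n = 99, (2/99)(0.75 − 0.25) = 0.0101. For n = 88, 0.0114.
- (c) Mean of 18 weekly scores, adjusted for baseline: v = (2/n)[(1+17ρ)/18 − ρ²]. For n = 99, (2/99)(0.528 − 0.25) = 0.0056. For n = 88, 0.0063.

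**Rule 1: each group judged by its own p-value.** Power in one group is p = Φ(d/√v − 1.96), and the chance that at least one of four is not significant is 1 − p⁴. Example for (b), n = 99, d = 0.3: √v = 0.1005, p = Φ(2.985 − 1.96) = 0.847, and 1 − 0.847⁴ = 0.485.

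| True effect, equal in all groups | (a) growth model | (b) two visits | (c) weekly |
|---|---|---|---|
| 0.2 SD | 98-99% | 93-95% | 66-74% |
| 0.3 SD | 76-83% | 48-58% | 8-13% |
| 0.4 SD | 32-41% | 8-14% | under 1% |
| 0.5 SD | 6-10% | about 1% | under 0.1% |

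In the other direction, with three groups gaining 0.5 SD and one gaining 0.25 SD, all four are significant in 46-52% (a), 64-70% (b) and 88-92% (c).

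**Rule 2: a 3-df interaction test.** With one group at zero and three at 0.3 SD, the non-centrality is 0.75 × 0.3²/v. For (b), n = 99, that is 0.0675/0.0101 = 6.7, giving power 57%. The test is non-significant in 59-63% (a), 43-49% (b) and 16-21% (c).

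**Sensitivity.** Aim 1 gives 420 per arm where Section 5.0 gives 440. On the smaller figure, the 0.3 SD entries become 52-62% for (b) and 10-16% for (c), which is little different. Analysis (c) is the least secure: exchangeability is optimistic for weekly scores, and applying both 70% compliance and 80-90% retention may count some missing data twice.

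**Set against the text.** Neither rule appears in the plan. The wording of Aim 1 can be read as one effect per group, but beside H2 it can equally be read as a comparison across groups. The missing H2 tag shows little, because H2 is H1's outcomes split by race and needs no instrument of its own. The tags are also loose: the Everyday Discrimination Scale and the social support questionnaire are tagged H3, although Section 1.0 puts discrimination and social support under H4.

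**The case for a change.** The best case for a change is that the gap is real on either reading of Aim 1. No interaction term, multi-group model, margin or interval criterion is named, race is absent from the listed moderators, and the only explicit comparison between race groups concerns experiences reported in the qualitative interviews. A paragraph written before results are seen would cost almost nothing, need no extra data, and close off a choice among analyses that behave very differently.

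The description of the text stands. The step from there to a fault does not. Section 20.0 points to analysis sections that are absent from the public file, and the H2 contrast would naturally sit there. Even without them, the growth models assigned to Aim 1 take a treatment-by-race term or a multi-group form as a matter of course, and four equal recruitment cells give balanced data for it.

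Nor would the obvious addition remove the discretion. Reporting each group against the mean of the other three, on four H1 measures at two visits, gives 4 × 4 × 2 = 32 unadjusted intervals with no positive rule for calling effects similar. Under a linear growth model the 3-month arm effect is exactly half the 6-month effect, so half of those intervals repeat the rest. The four contrasts also sum to zero, leaving three independent ones. Recasting H2 as purely descriptive would give up a stated prediction, which is a debatable trade rather than a correction.

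**Conclusion.** No change to the plan follows. The available text leaves the H2 comparison unspecified, but it adopts no faulty method. The missing step is one that analysts would ordinarily supply within the planned model: treatment-by-race terms, with each group's effect and the between-group differences reported with intervals.

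The numerical risk belongs to reading rules the plan does not state. It runs from under 1% to 99% across the assumed effect sizes and analyses, so it does not establish a defect of any particular size. At 0.3 SD it is 76-83%, 48-58% or 8-13% depending on the analysis, all conditional on ρ = 0.5, balanced arms within group and 80-90% retention. The figures do give a caution for reading the eventual report: neither a mix of significant and non-significant groups nor a non-significant interaction would by itself settle H2. The conclusion would be different if the plan had said that H2 would be decided by either of those rules.

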## 2.0 Background

**COVID-19 Racial/Ethnic Disparities.** Significant racial/ethnic health disparities have emerged in the United States (US) related to the novel 2019 SARS2-Coronavirus disease (COVID-19). Black and Hispanic persons experience significantly higher rates of COVID-19 relative to their proportion in the general population (19.9% and 31.4%, respectively), and the rate of COVID-19 cases is 2.6 and 2.8 times higher among Black and Hispanic persons, respectively, relative to Non-Hispanic White (NLW) persons. American Indian persons are 2.8 times more likely to contract COVID-19 relative to NLW individuals and are approximately 5.2 times more likely to be hospitalized from COVID-19 relative to NLW persons. Similarly, Black and Hispanic individuals are 4.7 times more likely to be hospitalized relative to NLW persons. Indeed, proportionate prevalence rates of COVID-19-related hospitalizations are highest among American Indian, Black, and Hispanic persons and lowest among

**FULL PROTOCOL TITLE:** Mobile Health to Monitor Risk for COVID-19 and Improve Mental Health during the Pandemic

NLW populations. Death from COVID-19 is 2.1 times higher among Black, 1.1 times higher among Hispanic, and 1.4 times higher among American Indian relative to NLW individuals. These data highlight the disproportionate, over-representation of BLAI individuals in COVID-19 infection rates, hospitalizations, and death relative to NLW individuals. Preexisting inequities related to social determinants of health and the effects of racism have likely contributed to these disparities.

BLAI individuals are more likely to be affected by COVID-19-related stress relative to NLW persons. Current rates estimate that 42.6% of Black and 46.3% of Hispanic individuals reported symptoms of an anxiety or depressive disorder between July 16-21, 2020. These estimates are in stark contrast to the estimated 11.3% of Black and 10.3% of Hispanic individuals who reported symptoms of an anxiety or depressive disorder from January - July 2019. Although NLW individuals experience comparable, albeit slightly lower, rates of anxiety or depression (38.8%), the racial/ethnic disparity gap for mental health outcomes is widening. To illustrate, data from 2019 found 0.2-1.2% difference in elevated anxiety or depressive symptoms between NLW and Black and Hispanic persons, with NLW individuals evincing a higher prevalence rate (11.5%). The inverse pattern is now true with Black and Hispanic persons reporting higher rates of these symptoms by 4-8 percentage points. These data offer valuable insight into the potential mental health disparities that are developing from the pandemic. Additionally, although post-pandemic onset mental health data for American Indians in the US is lacking, American Indian community leaders have expressed continued concern for the mental health of their constituents given their propensity for worse physical health outcomes if infected with COVID-19 and generally worse mental health outcomes, including high rates of substance use and suicide. Further, BLAI populations have lower access to mental health treatments and are less likely to engage with mental health treatments, which may compound the severity of emerging COVID-19-related mental health disparities. The pandemic has revealed changing mental health symptom patterns between BLAI and NLW, and emerging COVID-19 disparities in mental health symptoms are likely to widen without proper early intervention tactics.

**Chronic Stress and Health Disparities.** Impediments to care for BLAI individuals (e.g., racism, discrimination, mistrust of medical providers) and social determinants of health that make BLAI communities vulnerable to worse health outcomes (e.g., housing, income, access to healthcare) are known factors for chronic stress. Stressors are events or conditions that threaten, or are perceived to threaten, psychobiological equilibrium. From a psychophysiological perspective, stress activates the Hypothalamic-Pituitary-Adrenal (HPA) axis. The HPA axis' main function is to regulate the stress response. Continued and prolonged stress may disturb the HPA axis to the extent that negative feedback mechanisms are disrupted and may contribute to poorer health outcomes. This perspective is in line with the allostatic load theory, suggesting that continued stress can be associated with negative physical and mental health outcomes. Notably, BLAI individuals are at increased risk for high stress levels and greater chronicity of stress relative to NLW individuals, which accounts for a substantial portion of racial/ethnic health disparities. In the US, People of Color are more likely than NLW adults to report stress related to contracting COVID-19 (71% vs. 59%), accessing healthcare (59% vs. 46%), and meeting basic needs (61% vs. 47%). Chronic or repeated activation of the HPA axis often corresponds to prolonged or seemingly inescapable stressors, such as the present pandemic. As such, the additive effect of COVID-19-related disease and stress burden exerted on stress responses systems saturated with pre-existing chronic stress is likely to amount in worse short- and long-term mental health outcomes among BLAI communities.

**COVID-19 Stress Burden and Mental Health.** Exposure to COVID-19 stress likely influences the

**FULL PROTOCOL TITLE:** Mobile Health to Monitor Risk for COVID-19 and Improve Mental Health during the Pandemic

development, or exacerbation, of psychological and neurobiological processes that confer vulnerability to multiple types of psychopathology, including anxiety and depression. Anxiety and depression represent two of the most commonly experienced mental health conditions across race/ethnicity. In the following section, we describe a central stress-based, transdiagnostic mechanism that may underlie the link between COVID-19 stress and psychopathology, particularly anxiety and depression. Taking a transdiagnostic approach allows the identification of core psychological and neurobiological processes that underlie multiple forms of psychopathology. COVID-19 stress burden (accumulated impact of stress) may have a particularly pernicious influence when it happens among persons already struggling with greater stress exposure and pre-existing psychopathology. Specifically, higher degrees of COVID-19 stress can influence patterns of social, emotional, and neurobiological development in ways that facilitate the rapid detection of potential threats, and by extension, may increase risk for multiple forms of psychopathology.

**Importance of Stress and Stress Reactivity.** Adverse life events increases the risk of psychopathology, particularly disorders of emotion. Indeed, alterations in stress- and threat-response systems may compromise emotion-and attention-regulatory systems. These data have often been used to explain the heightened risk for behavioral and affective disorders following exposure to adverse stressors in life. This transdiagnostic theoretical framework also is at the crux of the assertion that increased rates of emotional disorders are an inevitable consequence of the pandemic. After repeated exposure, a threat processing system involving a rapid appraisal-response system develops that is capable of orchestrating rapid reactions with little processing. Thus, individual differences in the tendency to be ‘stress reactive’ (i.e., appraise threat rapidly) provide a fertile theoretical and clinical basis for understanding the nature of COVID-19 stress on emotional disorders among BLAIs specifically (see A.4.b).

**Anxiety Sensitivity.** Research in affective science has identified anxiety sensitivity (AS) as an ‘affect amplifier’ because it represents a fundamental threat appraisal process. Specifically, AS refers to the fear of anxiety symptoms, including bodily sensations, which results from beliefs about the harmful social, psychological, or physiological consequences of such symptoms. AS has consistently been identified as a malleable risk factor for the onset of panic attacks, panic disorder, generalized anxiety, depression, and posttraumatic stress, in prospective studies of adults across race/ethnicity. Specifically, AS has been found to predict the development of panic attacks and has been linked to panic-like symptoms, anxiety, fear, and clinical anxiety and depressive disorders across a range of diverse community and clinical samples. It is important to note that AS predicts anxiety symptoms above and beyond trait anxiety, demonstrating the incremental validity of this construct. AS also has demonstrated strong racial/ethnic invariance across a range of samples, including BLAI groups. Individuals with high AS may be more likely to attend to bodily sensations that are associated with anxiety, such as respiratory symptoms, stomach distress, fatigue, and body aches, and to misinterpret these symptoms as dangerous or catastrophic. These interpretations of bodily sensations can lead to increased anxiety and perpetuate a cycle of increased attention to and misinterpretation of bodily cues. This process may eventually lead to avoidance and increased symptoms of anxiety, stress, and depression, and it has the potential to exacerbate stress on the body systems, which, in turn further compromises the immune system and places individuals at risk. This maladaptive cycle may be particularly relevant to BLAI populations during the pandemic given their increased likelihood of COVID-19 exposure, challenges with enacting behaviors to reduce the likelihood of infection, concerns about the increased likelihood of worse outcomes if infected, and

**FULL PROTOCOL TITLE:** Mobile Health to Monitor Risk for COVID-19 and Improve Mental Health during the Pandemic

greater pandemic-related stress (e.g., job loss, income reduction, childcare needs). Further, because some BLAI populations experience psychological distress somatically, AS is particularly relevant to these groups because it amplifies threat response to somatic perturbation.

**AS Relevance for BLAI Individuals.** AS is highly theoretically relevant to BLAI individuals based on several lines of work. First, BLAI individuals have increased awareness of the negative outcomes of physical symptoms and illnesses. Second, BLAIs experience more somatic symptoms, and are more distressed by these symptoms compared to NLW persons. Third, BLAI individuals are more often diagnosed with comorbid psychiatric disorders than NLWs. Finally, affective disturbances are associated with an increased prevalence of comorbid medical diseases, such as chronic pain, arthritis, and cardiovascular disease, and many of these chronic medical conditions disproportionately affect BLAIs. Thus, interrelated lines of work suggest that BLAI populations may be more apt to react to interoceptive symptoms with heightened anxiety and mood disturbances. Yet, past work has not leveraged the potential of AS to better address mental health inequalities in the context of the pandemic which represents a unique and unprecedented period that may contribute to increased mental health disparities.

**AS: Precision Medicine Treatment Target.** Approaches to break the link between AS-anxiety/stress/depression have been developed and have demonstrated strong efficacy. Indeed, AS is malleable in response to psychosocial intervention, making it a prime mechanistic agent to target in prevention/intervention programs. Reductions in AS improve clinical outcomes among general clinical and nonclinical populations, highlighting the relevance of this construct within the general population. AS reduction treatment can be distilled in as few as 1-4 treatment sessions both in-person or via computer, with equal success. AS treatment decreases AS by providing psychoeducation about the true dangers of anxiety related bodily sensations; cognitive restructuring of catastrophic appraisals of anxiety related bodily sensations and life experiences; and by helping individuals develop greater tolerance to these sensations through interoceptive and in vivo exposure exercises. Such decreases, in turn, result in reduced anxiety, depression, and related conditions (e.g., stress burden). Thus, a cognitive-behavioral approach that targets maladaptive cognitions about bodily symptoms (i.e., AS) may have significant clinical utility in decreasing anxiety and depressive symptoms in the context of COVID-19. Indeed, COVID-19 stress and associated beliefs for exposure and health-risk associated with COVID-19, which is likely to be elevated among BLAI persons, may motivate vigilance to internal sensations. COVID-19 may thus serve as a context in which individuals learn to fear bodily sensations because such sensations could potentially have harmful consequences. Yet, intervention work to address the impact of AS on mental health outcomes among BLAI individuals has not been leveraged in the context of COVID-19 stress.

